In the Bonner trial and in the Vermorken study there was an increased survival benefit that was associated with oropharynx sites. High risk HPV (human papilloma virus) infection has been implicated both as an etiologic factor and as a prognostic factor for survival and response to therapy. HPV is also typically associated with a younger cohort of patients, however as the high risk HPV infected cohort ages, we do expect to see more patients in their 70s and beyond who will have HPV-related head and neck cancers. Thus, we postulate the EGFR inhibition will work better in HPV positive tumors. We will investigate the presence of HPV in the tumor tissue biopsies by a variety of assays. We will also examine the p53 status using RNA isolated from the tumor biopsy since HPV positive tumors most frequently have wild type p53 which may also contribute to the high response rate of these tumors.

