### 2.2 Secondary

- 2.2.1 Conduct normal mucosa EGFR assessment for comparison with tumor sample.
- 2.2.2 Correlate HPV presence and titer with p53 status and clinical outcome.

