#### 13.5

##### Method of Assessment of EGFR Expression in Tumor After Cetuximab

##### Loading Dose

At the time of the second biopsy, four core biopsies from different areas of the tumor as well as swab of the normal appearing mucosa will be obtained. Four core biopsies will be processed with one core used in high-throughput immunoblot analysis, one core will be fixed in formalin to be embedded in paraffin, one core will be frozen and fixed in Tissue-Tek OCT for immunofluorescence analysis and one core will be used for RNA and DNA isolation using Trizol. EGFR phosphorylation analysis using immunoblotting and immunohistochemistry will be performed in the surgical specimen and immunofluorescence analysis will also be performed if sufficient tissue is available using standard methods. Interpretations of the staining will be performed according to the standard guidelines. The EGFR and critical associated down-stream signaling pathways will be analyzed post- induction therapy, including p-EGFR and total EGFR, p-ERK1/2, p-AKT, p27, Ki-67, and p-STAT3, and other markers that we may discover in our preclinical studies. EGFRvIII expression and p53 mutation analysis will be assessed on cDNA obtained from total RNA converted with RT-PCR. Genomic DNA from the tumor biopsy will be used to test for HPV presence and type as carried out by PCR-mass spect using the AttoSense assay at SensiGen, LLC.

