dichotomous scale; markers measured on a continuous scale will be analyzed via general linear models (possibly after transformation), while ordinal and dichotomous markers will be analyzed via cumulative logit and logistic regression analyses, respectively. The primary questions to be answered in this objective are: is the marker modulated by the loading dose of cetuximab; are there baseline clinical or demographic variables that are related to significant variation in biomarker response to the loading dose of cetuximab? For continuous variables, the null hypothesis that the mean value of the change (absolute or percent of baseline) equals zero will be tested by means of a single sample t-test. The second question will be answered by means of analysis of variance on baseline clinical and demographic variables. For dichotomous markers, patients will be stratified into elevated versus not elevated at baseline, and Wald tests on logistic regression parameter estimates will be used to test the null hypothesis that the proportion of patients changing state from baseline is different from 0.5, and to determine if any subset of patients defined by clinical or demographic factors have proportions significantly different from 0.5. Ordinal markers will be handled in a similar fashion.

[figure not shown]
21.3.2 **Primary Objective 2** Characterize clinical outcomes, including local recurrence, progression-free survival and overall survival in these patients, and correlate these clinical outcomes with the changes in tumor EGFR, pEGFR, downstream signaling, and novel phosphoproteins. Logistic regression and proportional hazards (Cox) regression will be used to relate clinical out (local recurrence, progression-free survival or overall survival) to changes in markers across the loading dose. All of the markers will be analyzed, but markers that are modulated by the loading dose (identified in Primary Objective 1) will be of particular interest.

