21.3.3 **Primary Objective 3** *Describe the toxicity, in particular mucositis/dysphagia, of this regimen.* Adverse events will be tabulated by grade (NCI CTCAE v4), category (mucositis and dysphagia are expected to be the most common) and relatedness to treatment (not, unlikely, possibly, probably or definitely). The proportion of patients experiencing Grade 3 or worse adverse events at least possibly related to treatment will be calculated, accompanied by a 95% exact binomial confidence interval. Possible baseline demographic and clinical predictors of such toxicity may be evaluated by means of logistic regression, but, due to the low expected number of such toxicities, any such modeling will be strictly exploratory.

21.3.4 **Secondary Objective 1** *Conduct normal mucosa EGFR assessment for comparison with tumor sample.* The change in tumor EGFR level across treatment, relative to EGFR in normal mucosa, will be evaluated by means of repeated measures ANOVA.

21.3.5 **Secondary Objective 2** *Correlate HPV presence and titer with p53 status and clinical outcome.* HPV status ( $\pm$ ) will be added to the models of Primary Objective 2 to determine if +HPV patients respond to therapy differently than -HPV patients, but, due to the limited expected number of +HPV patients, such analyses will be considered exploratory.

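### The HPV term in the 21.3.5 outcome models cannot show a different response to cetuximab, and the complementary comparison of Day 7 marker change by HPV status is not specified

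*Combined protocol and SAP*

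**What the plan says.** Section 1.1 notes that in two earlier cetuximab studies "there was an increased survival benefit that was associated with oropharynx sites", describes HPV as prognostic for survival and for response to therapy, and concludes: "Thus, we postulate the EGFR inhibition will work better in HPV positive tumors".

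Objective 2.2.2 is to "Correlate HPV presence and titer with p53 status and clinical outcome". Section 21.3.5 carries this out by stating that HPV status (+/-) "will be added to the models of Primary Objective 2 to determine if +HPV patients respond to therapy differently than -HPV patients". It adds that "due to the limited expected number of +HPV patients, such analyses will be considered exploratory". The models it refers to, in 21.3.2, are logistic and Cox regressions relating local recurrence, PFS or overall survival "to changes in markers across the loading dose".

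Marker change has its own analysis in 21.3.1, which asks "are there baseline clinical or demographic variables that are related to significant variation in biomarker response to the loading dose of cetuximab". The variables are not listed and HPV is not mentioned.

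The data for the comparison are planned. Section 21.2 makes both research biopsies a condition of being evaluable. Section 7.3 places the second biopsy about 7 days after the loading dose and before radiation. Section 13.5 states: "Genomic DNA from the tumor biopsy will be used to test for HPV presence and type".

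**The concern.** Two features of the planned HPV term limit what it can say.

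First, all patients receive cetuximab with radiation. If HPV-positive patients do better, the cause may be the favourable prognosis that section 1.1 already attributes to HPV, a larger effect of cetuximab, or both. No contrast in this design separates them. The wording of 21.3.5 nevertheless promises an answer about response to therapy.

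Second, the term is added to models that already contain the change in an EGFR-pathway marker. It therefore estimates the HPV association at a given marker change. If HPV status improved outcome through deeper EGFR inhibition, that part would be adjusted away. No HPV-by-marker interaction is specified either.

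The marker-change data bear on the postulate from another side. They follow cetuximab alone, before radiation, with each patient as his or her own control. No section names HPV as a factor in that analysis. At stake is the reading of a secondary objective: an HPV coefficient could be reported as differential response to cetuximab, while a relevant comparison on the same patients depends on whether someone thinks to run it.

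**Working it through.** **Inputs.** From 21.4: 50 patients, 36 months' accrual, analysis 6 months after the last patient, median 22 months, alpha 0.05. Assumed: exponential PFS, uniform accrual, two-sided test. The HPV-positive count is not given, so 3 to 20 of 50 is taken as an assumed range.

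**The plan's own figure.** Section 21.4 states at least 80% power for a marker difference of 1.1 SD between patients with PFS below and above the median. A simulation on those inputs (Cox Wald test, 20,000 runs) gives 77% at 1.0 SD, 82% at 1.05 and 84% at 1.1. The statement reproduces and is not in dispute.

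**Expected events in that scenario.** λ = ln 2 / 22 = 0.0315 per month. Events = 50 × [1 − (e^(−6λ) − e^(−42λ)) / (36λ)] = 50 × [1 − (0.828 − 0.266) / 1.134] ≈ 25.2.

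**HPV against Day 7 change, one marker.** With m HPV-positive patients, the difference detectable with 80% power is about (1.960 + 0.842) × √(1/m + 1/(50 − m)) SD. For m = 10: 2.802 × 0.354 = 0.99. For m = 5: 2.802 × 0.471 = 1.32. The exact calculation (noncentral t, 48 df) gives 1.01 and 1.35. The expected 95% CI half-width is about 2.011 × the same square root: 0.71 SD for m = 10 and 0.95 SD for m = 5.

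**HPV against PFS.** With p = m/50, the hazard ratio needed for 80% power is exp(−2.802 / √(25.2 × p(1 − p))). For m = 10: exp(−2.802 / 2.01) = 0.25.

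| HPV-positive of 50 | Marker difference for 80% power (SD, exact) | Power at 1.1 SD | PFS HR for 80% power | Power at assumed HR 0.5 |
|---|---|---|---|---|
| 3 | 1.70 | 44% | 0.10 | 13% |
| 5 | 1.35 | 63% | 0.16 | 18% |
| 8 | 1.10 | 80% | 0.22 | 25% |
| 10 | 1.01 | 86% | 0.25 | 29% |
| 15 | 0.88 | 94% | 0.30 | 36% |
| 20 | 0.83 | 96% | 0.32 | 40% |

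**Two sensitivities.**
- Many markers: with 10 markers (assumed) and a Bonferroni correction, the multiplier becomes 2.807 + 0.842 = 3.649. For m = 10 the detectable difference rises to 3.649 × 0.354 = 1.29 SD (normal approximation).
- Longer follow-up: section 8.0 follows disease status and survival to year 5. With 60 months on every patient, events = 50 × (1 − 2^(−60/22)) ≈ 42. For m = 10 the required HR moves from 0.25 to exp(−2.802 / √(42.4 × 0.16)) ≈ 0.34.

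Standard deviations of marker change and hazard ratios are different scales, so the columns do not rank the two analyses. They show that the outcome term can detect only very large HPV associations, and that the marker comparison is informative with about 8 or more HPV-positive patients and weak with 3 to 5.

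**The case against.** The best defence is that 21.3.5 does what its objective asks. Objective 2.2.2 names clinical outcome, and 21.3.5 models clinical outcome. The postulate in 1.1 is drawn from survival benefit and response, so working better most naturally means clinical efficacy there. This stands. A reader might infer that outcome is the wrong dependent variable; the documents do not support that. Elsewhere (sections 1.3 and 13.0) the protocol does use inhibition in a molecular sense, so the marker comparison is relevant, but as a complement.

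Nor would marker change settle the postulate. Section 1.3 says benefit may also require that the tumour depends on the pathway, so equal inhibition in both HPV groups would be compatible with unequal benefit. Whether marker change predicts outcome is itself a hypothesis of this trial. The inference that Day 7 change is the HPV question this trial can best answer therefore goes too far.

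A reader might also infer that HPV and marker change will go unanalysed. The covariate list in 21.3.1 is open and could take in HPV. The accurate statement is that the comparison is not specified.

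Finally, 21.3.5 already labels the HPV analyses exploratory. That limits the weight given to a small-sample result. It does not address attribution: a precise HPV coefficient from a single arm would still not distinguish prognosis from cetuximab effect.

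**Conclusion.** The point holds in a limited form. The HPV term in 21.3.5 is an association with outcome, conditional on marker change, from a single arm. It cannot show that HPV-positive patients respond differently to cetuximab. That conclusion follows from the design and model and does not depend on any assumed number.

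The comparison of Day 7 marker change by HPV status is unspecified although the data for it are planned. For a single marker at two-sided 0.05, with all 50 patients contributing, it has 80% power for about 1.0 SD if 10 are HPV-positive and about 1.35 SD if 5 are. These figures rest on an assumed HPV-positive count, make no allowance for multiple markers, and worsen if assays fail. The result would be exploratory on any of these counts.

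No primary analysis, sample size or safety provision is affected.

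**What to change.** Keep the outcome analysis in 21.3.5 and amend the text in two places.

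1. Name HPV status (+/-) as an exploratory factor in the 21.3.1 models for change in EGFR, pEGFR and the downstream markers. Report the HPV difference in change with a 95% CI for each marker (on the odds-ratio scale for ordinal or dichotomous markers), together with the numbers of HPV-positive and HPV-negative patients and the number of markers examined.
2. Replace the statement about responding differently to therapy. Say that the HPV term in the Primary Objective 2 models is an association with outcome, to be read as prognostic, and is not evidence of a different response to cetuximab. Report it with and without marker change in the model.

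The cost is a wording change and one additional exploratory model per marker, plus the outcome models refitted without marker change. No new samples, visits or patients are needed.

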## 23.0 Appendix

### Appendix A

### **KARNOFSKY PERFORMANCE SCALE (KPS)**

100	Normal; no complaints; no evidence of disease
90	Able to carry on normal activity; minor signs or symptoms of disease
80	Normal activity with effort; some sign or symptoms of disease
70	Cares for self; unable to carry on normal activity or do active work
60	Requires occasional assistance, but is able to care for most personal needs
50	Requires considerable assistance and frequent medical care
40	Disabled; requires special care and assistance
30	Severely disabled; hospitalization is indicated, although death not imminent
20	Very sick; hospitalization necessary; active support treatment is necessary
10	Moribund; fatal processes progressing rapidly
0	Dead

## Appendix B

### **Sample Collection and Analysis**

Both pre- and post-treatment punch-biopsy specimens (about 3x3x3 mm) of the tumor will be collected and immediately placed in ice-cold saline containing a cocktail of protease (Roche Diagnostic Co., Indianapolis, IN) and phosphatase inhibitors (Sigma, St. Louis, MO). The sample will be then divided into three parts:

1. The first part will be fixed in formalin and will be used for the construction of a tissue microarray.
2. The second part will be homogenized and total proteins will be directly extracted using Laemmli buffer for immunoblotting.
3. The third part will be used for DNA and RNA extraction for assessment of HPV, p53 status and EGFRvIII expression.

In addition, Tunnel assay will also be performed to analyze the apoptosis in all the samples under investigation.

### **High-throughput immunoblotting and isolation of RNA and DNA for genetic studies:**

Tumor samples are collected and immediately stored in Allprotect Tissue Reagent from Qiagen. They are then divided and one portion is homogenized for protein extraction 45, 46. A total of 200 µg total protein will be subjected to electrophoresis on a 2D 4 to 12% bis-tris precast gel (Invitrogen, Carlsbad, CA) and transferred onto a PVDF membrane. A Miniblotter 28 dual system (Immunelect, Cambridge, MA) will be used to probe all the antibodies in duplicate. After incubating the membrane with different antibodies overnight, membranes will be washed and probed with horseradish peroxidase conjugated IgG (Cell Signaling Technology, Beverly, MA), diluted 1:25,000 in TBST for 1 hr at room temperature; the antigen-antibody complexes will be visualized by enhanced chemiluminescence (ECL-Plus; GE Biosciences, Piscataway, NJ). The films then will be scanned, and the bands analyzed using NIH ImageJ software. Proteins to be assessed include phospho and total forms of EGFR, AKT, Src, STAT3, in addition to total p27, PARP, Bcl-XL and novel proteins for which we have either commercially available or custom-raised antibodies. Isolation of DNA and RNA will be carried out using DNAeasy and RNAeasy (both from Qiagen) on the remaining sample according to the manufacturers instructions.

### **Apoptosis Determination:**

TUNEL assays will be performed using the In Situ Cell Death Detection Kit (Roche Molecular Diagnostics, Laval, Quebec, Canada). Slides will be evaluated by two investigators and three areas from each core will be identify based as -, +, and +++ based on relative staining intensity. These selected areas will be lifted to build a tissue micro-array for the analysis of the specific effects of treatment and to understand the mechanism of action of the cell death.

### **Immunohistochemistry and Scoring of TMA:**

Antigen is retrieved from formalin-fixed tumor sections, in citrate buffer using a pressure cooker. Standard procedures are used for immunofluorescence. One high-density TMA will be constructed using a manual tissue arrayer (Beecher Instruments, [name], USA) at the core facility at the University of Michigan using standard methods. Tissue cores from the regions of interest (tumor

tissues, before and after treatment) will be targeted for transfer to the recipient array block. At least three 0.6 mm diameter replicate tissue cores will be sampled from each subregion of the selected sample. The final TMA will consist of approximately 200 cores. After construction, 4  $\mu$ m sections will be cut, and hematoxylin and eosin staining will be performed on the initial slide to verify the histology. Serial 4  $\mu$ m sections will be further cut and transferred to positively charged slides, these sections will be subjected to standard immunohistochemical staining procedures. Use of this established core enables the investigators to have access to over 200 commercially available antibodies that have been tested and validated for immunohistological use. Any antibodies not previously validated will be tested on slides made from "test arrays". These are tissue microarrays prepared from multiple tissue sources (e.g. normal mucosa, skin, brain, lymph nodes, gut, lung, spleen, liver, kidney etc., plus corresponding neoplastic tissues) created by the UM Cancer Center Tissue Procurement Core and available to the investigators. The stained test slides will be reviewed by certified pathologist for the expected pattern and appropriate intensity. The information about expected and appropriate staining for each antibody will be discussed with the other investigators to confirm the scoring criteria. The TMAs will be then stained by the staff at the Tissue Core. Each tissue core will be scored by a board certified oral and maxillofacial pathologist who is blinded as to the identity of the cores. Each tissue core will be scored for intensity of SCC cells staining: 1, undetectable; 2, weak; 3, moderate; 4, strong. An example of TMA cores is shown in Figure 2. Data analysis will be performed by [name]. Multiple TMA core measurements from the same subject will be averaged. This average score in its continuous scale will be used in all analyses.

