#### **Immunofluorescence studies:**

Immunofluorescence studies are semi-quantitative and are to be used if available antibodies do not perform well for quantitative immunohistochemical analysis. For this purpose high-resolution grey scale images are captured using a fluorescent microscope equipped with a Hamamatsu camera (Hamamatsu, Japan). The relative intensities of fluorescence are obtained using Wasabi software (Bridgewater, N.J).

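### The tissue-array score records staining intensity only, so for Ki-67 a fall in the share of stained tumour cells may be missed or blunted

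*Combined protocol and SAP*

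**What the plan says.** Section 13.5 lists the markers to be examined after the loading dose, "including p-EGFR and total EGFR, p-ERK1/2, p-AKT, p27, Ki-67, and p-STAT3", together with any others found in preclinical work. It does not tie Ki-67 to a particular assay.

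Appendix B then describes the assays.

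- **Tissue array.** The rule is "Each tissue core will be scored for intensity of SCC cells staining: 1, undetectable; 2, weak; 3, moderate; 4, strong". Repeat cores from one patient are averaged, and "This average score in its continuous scale will be used in all analyses". The reader is a pathologist blinded to core identity.
- **Immunoblot.** The list reads "Proteins to be assessed include phospho and total forms of EGFR, AKT, Src, STAT3, in addition to total p27, PARP, Bcl-XL and novel proteins". Ki-67 is not named.
- **Immunofluorescence.** This is a fallback, "to be used if available antibodies do not perform well for quantitative immunohistochemical analysis", and its output is again intensity: "The relative intensities of fluorescence are obtained using Wasabi software".

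No section calls for a percentage of positive cells, a labelling index or a score combining share and intensity.

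Section 21.3.1 asks whether each marker is modulated by the loading dose. Section 21.3.2 relates marker change to local recurrence, progression-free survival and overall survival.

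**The concern.** A marker can change in two ways: the stained cells become paler or darker, or the share of cells that stain goes down or up. The array rule has a place for the former only.

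Ki-67 is the marker for which this matters most. The premise, which the protocol does not state, is that Ki-67 marks cycling cells, so that reduced proliferation shows mainly as fewer positive cells and not as weaker staining of those that remain positive. On that premise the recorded score can move less than the biology does, or not at all.

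At stake are the Ki-67 answers under Primary Objectives 1 and 2: whether cetuximab changed proliferation in the tumour, and whether that change relates to outcome. The shortfall lies in what is recorded, so an analyst could not repair it later without having the slides read again.

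**Working it through.** **1. The plan's own figure.** Section 21.4 claims at least 80% power at an effect of 1.1 standard units. The inputs are 50 patients, 36 months of accrual, a 22-month median, analysis six months after the last patient, and alpha 0.05 (taken as two-sided). Simulating this design with exponential times and a Cox Wald test, 3,000 runs per point and about 25 events, gives 83% at 1.1 and 78% at 1.0. The claim reproduces. It concerns a normally distributed marker and contains no scoring step, so it does not measure the present issue.

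**2. Which assay covers which marker in Section 13.5.**

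| Marker | Named on the immunoblot list? | Array reading |
|---|---|---|
| EGFR, AKT, STAT3 (phospho and total) | Yes | Intensity, 1 to 4 |
| p27 | Yes (total) | Intensity, 1 to 4 |
| p-ERK1/2 | No, but Section 13.0 says downstream signalling markers are measured by immunoblotting as well as immunohistochemistry | Intensity, 1 to 4 |
| Ki-67 | No | Intensity, 1 to 4 (natural reading; not expressly assigned) |

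A blot of homogenised tissue reflects total protein, so it responds when fewer cells express the marker. The markers on the blot list therefore have a second reading that picks up a change in share. Ki-67 has none that is named.

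**3. What the score does when only the share changes.** The values are assumed for illustration: positive SCC cells are strong (4), the rest are undetectable (1), and the share positive, p, falls from 60% to 30%. Appendix B does not say how a mixed core is turned into one number. Three ways are possible.

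- *Grade the stained cells.* 4 before, 4 after: recorded change 0.
- *Grade the average over all SCC cells, to the nearest whole number.* The mean is 4p + 1(1 − p) = 1 + 3p. Before: 1 + 3(0.60) = 2.8, scored 3. After: 1 + 3(0.30) = 1.9, scored 2. Recorded change −1. Under this reading a score of 3 covers 2.5 ≤ 1 + 3p < 3.5, that is p from 50% to about 83%, and movement inside that band does not show on a single core.
- *Grade the commonest appearance.* Before, most cells are strong: 4. After, most are undetectable: 1. Recorded change −3. Any fall that stays above 50% is recorded as 0.

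The same halving of positive cells is recorded as 0, −1 or −3. A percent-positive reading records −30 points whichever way intensity is judged.

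**4. Why no loss of power is quoted.** Converting this into power needs the relation between the recorded score and the true change. That relation depends on which reading is used and on how Ki-67 varies between patients. The documents give neither.

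**The case against.** The strongest reply is that the plan leaves room for a suitable Ki-67 reading. Section 13.5 says "Interpretations of the staining will be performed according to the standard guidelines". Appendix B says that expected staining for each antibody will be "discussed with the other investigators to confirm the scoring criteria". Section 13.4 expects sections for immunohistochemistry in addition to array cores. Ki-67 is never expressly assigned to the array, and the blot list is introduced as inclusive and admits novel proteins. All of this is correct, and it is why the point is put as a likely weakness and not a certain one. None of these texts mentions the share of stained cells, however, and the one explicit scoring rule is intensity only.

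A second reply is that Ki-67 is a minor marker. It is named once, in Section 13.5. It is absent from the objectives in Section 2.1 and from the candidate predictors in Section 1.3. This stands, and it limits the point to one marker.

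Stronger readings are tempting, and the documents do not support them:

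- A reader might infer that p27 and p-ERK1/2 are left in the same position. Total p27 is on the blot list, and Section 13.0 plausibly puts p-ERK1/2 on immunoblot.
- A reader might infer that a real effect on proliferation would be reported as no modulation. That follows only if the pathologist grades stained cells alone, which Appendix B does not say.
- A reader might infer that every array marker needs a combined share-and-intensity score. Most of them have a blot reading, and nothing in the plan shows that intensity is inadequate for them.

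**Conclusion.** The point holds for Ki-67. Followed as written, the plan records intensity and not the share of stained cells, and names no other assay that would capture that share. A fall in positive cells may be missed or blunted, which weakens the Ki-67 part of Primary Objectives 1 and 2. It does not undermine those objectives as a whole: most of the other signalling markers are on the immunoblot list.

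The conclusion rests on two assumptions: that Ki-67 is to be read on the array, and that its response lies mainly in the share of positive cells. The size of the loss is not known and cannot be derived from the documents. This is an inexpensive improvement to make before the array is read, not a fault that invalidates the design.

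**What to change.** In Appendix B, under the array scoring rule, add that for Ki-67 the same blinded pathologist also records the percentage of SCC cells stained on each core. State that this percentage is averaged over a patient's cores and that percent positive is the Ki-67 analysis variable for Sections 21.3.1 and 21.3.2. Keep the intensity score for the other markers. If Ki-67 is meant to be read by another assay, name that assay instead.

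The cost is one more reading per core for one marker. Appendix B puts the array at approximately 200 cores, so about 200 extra readings. Should all 50 patients supply three cores from each of two biopsies, the number would be 50 × 2 × 3 = 300. No extra tissue, patients or readers are needed.
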